6.1.2.8. Change from Baseline in FACIT-fatigue

The FACIT-Fatigue score (V4.0 16Nov2007) is derived by taking the sum of the scores for the 13 questions in the instrument, resulting in a score between 0 and 52. The questions consider the patients functionality over the 7 days prior to completing the questionnaire. Higher scores represent better patient status (less fatigue).

For some of the questions, the scale indicates a higher score is better and for others, a lower score is better. Therefore, in order to ensure that higher scores represent better status, the items marked with a ‘-’ in table 4 below will be reversed by subtracting the response from “4” before summing all subscale items to derive the FACIT-Fatigue score. **Table 4. FACIT-Fatigue**

Item No.	Question	+/-
HI7	I feel fatigued	-
HI12	I feel weak all over	-
An1	I feel listless (“washed-out”)	-
An2	I feel tired	-

PFIZER CONFIDENTIAL

An3	I have trouble starting things because I am tired	-
An4	I have trouble finishing things because I am tired	-
An5	I have energy	+
An7	I am able to do my usual activities	+
An8	I need to sleep during the day	-
An12	I am too tired to eat	-
An14	I need help doing my usual activities	-
An15	I am frustrated by being too tired to do the things I want to do	-
An 16	I have to limit my social activity because I am tired	-

See [Section 7.1.3](#) for details on the rules for deriving the FACIT-Fatigue score if there is missing data.

The FACIT-Fatigue score will be derived at each time point (Baseline, Month 3, 6 and 12) and the change from baseline calculated for Month 3, 6 and 12.

6.1.2.9. Change from Baseline in Morning Stiffness

The duration of morning stiffness is measured in minutes and is collected at all time points (Baseline, Month 3, 6 and 12).

6.1.2.10. Change from Baseline in WPAI

The Work Productivity and Activity Impairment (WPAI, V2.0 15Jan2007) questionnaire consists of 6 questions, from which scores are derived for four domains; absenteeism, presenteeism (impairment at work/reduced job effectiveness), work productivity loss and activity impairment. These are calculated as percentage impairment as follows:

1. Absenteeism = $(Q2 / (Q2 + Q4)) * 100$
2. Presenteeism = $(Q5 / 10) * 100$
3. Work Production Loss = $\{ ((Q2 / (Q2 + Q4)) + [(1 - (Q2 / (Q2 + Q4))) * (Q5/10)] \} * 100$
4. Activity Impairment = $(Q6/10) * 100$

Note that higher numbers indicate greater impairment and less productivity.

A domain score can not be calculated if there is a missing response to the items required to derive the score (http://www.reillyassociates.net/WPAI_Coding.html).

WPAI scores are based on 1-item (presenteeism, activity impairment), 2-items (absenteeism) and multiple items (overall work productivity); a score can not be calculated if there is a missing response to the corresponding item. An analysis of

absenteeism would include only those subjects with responses to hours missed and to hours worked; an analysis of presenteeism would include only those subjects with a response to productivity while working. For the analysis of overall work productivity, scores can only be calculated for subjects with responses to hours missed, hours worked and productivity while working.

See [Section 7.1.4](#) for the handling of missing data in the analysis of WPAI.

The percentage impairment will be derived for each domain at each time point (Baseline, Month 3, 6 and 12) and the change from baseline calculated for all post-baseline timepoints (Month 3, 6 and 12).

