9.9. Limitations of the Research Methods

Randomised controlled trials are important and powerful tools in assessing efficacy and safety but have their limitations in terms of generalisability. In order to assess health economics, clinical effectiveness and safety of Tofacitinib in a usual care setting, parameters need to be determined by performing observational studies.

Limitations of non-interventional, observational, non-controlled, non-randomised studies in general are the risk of selection/ascertainment bias and some lack of a parallel control group, which complicate the interpretation of the causality between treatment and outcomes.

Furthermore, as with any "as observed" analysis, there is a potential risk of bias due to missing outcome data; the risk increases with increasing number of missing outcome data.

As data captured will be limited to information available from the physician participating in the study under a usual care setting, there is a greater possibility that there will be individual items of missing data (eg, CRP not measured or questionnaires not completed).

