7.1. Patient Reported Outcomes (PROs)

For the questionnaires that will be used in the study (EQ-5D, HAQ-DI, FACIT-Fatigue and WPAI), the rules for replacing missing values suggested by the producers of these questionnaires will be followed. If these rules result in the patient having a missing score at a visit, then the missing values will be assumed to be missing at random. Further details of the missing data rules from the relevant scoring guidelines are provided below.

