7.1.4. WPAI

A domain score can only be calculated if none of the required items have missing data. If any of the required items have missing data the domain score will be set to missing. Missing data will not be imputed.

8. STATISTICAL METHODOLOGY AND STATISTICAL ANALYSES**8.1. Statistical methods****8.1.1. Logistic Regression Analysis**

The potential role of several baseline clinical and biochemical parameters as independent predictive factors of remission or LDA will be investigated using logistic regression. The potential predictive factors to be considered are described in [Section 6.4](#).

The effect of each factor will firstly be tested with a univariate logistic regression model. All potential factors with a p-value resulting from univariate analysis less than 10% will then be included in a multivariate model, along with any factors considered important from a clinical point of view. Predictive factors and their interactions will be chosen using a backward (step-down) selection. Predictive factors chosen will be those which have a p-value less than 5%. In the case of a significant interaction, all individual components of the interaction will be “forced” in the model, whether they are statistically significant or not.

The SAS procedure PROC LOGISTIC will be used to perform the logistic regression analyses.

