8.1.2. Analysis of Continuous Data

Unless specified otherwise, continuous variables will be summarised using descriptive statistics (n, mean, standard deviation (SD), median, min, max).

The change from baseline in EQ-5D ([Section 6.1.2.7](#)), FACIT-Fatigue Scale ([Section 6.1.2.8](#)), WPAI ([Section 6.1.2.10](#)) at each time point will be analyzed using mixed models for repeated measures (MMRM), with time-point as a fixed effect; the baseline value will be entered in the model as a covariate, alongside the baseline by time-point interaction. Any missing observations will be set to missing and the MMRM model will assume data are missing at random. Subjects will be fitted as a random effect where an unstructured covariance structure will be used to model the within-subject errors. The Kenward-Roger

approximation will be used to estimate denominator degrees of freedom. If the model fails to converge autoregressive 1 will be fitted instead.

The SAS procedure PROC MIXED will be used to perform the MMRM analysis.

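### The WPAI scoring rule discards a work productivity loss score that is already fixed at 100% if a patient who worked no hours leaves Q5 blank

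*SAP*

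**What the plan says.** SAP 6.1.2.10 derives four WPAI domains. Absenteeism is the ratio of hours missed (Q2) to hours missed plus hours worked (Q4). Presenteeism is Q5/10. Work productivity loss adds to the absenteeism fraction the remaining fraction multiplied by Q5/10. Activity impairment is Q6/10. Each is expressed as a percentage, and "higher numbers indicate greater impairment and less productivity". Protocol 9.7.3.4.2 gives the same formulas.

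For overall work productivity, SAP 6.1.2.10 states that "scores can only be calculated for subjects with responses to hours missed, hours worked and productivity while working". SAP 7.1.4 repeats the rule for every domain: "If any of the required items have missing data the domain score will be set to missing", and "Missing data will not be imputed". SAP 7.1 gives the basis: "the rules for replacing missing values suggested by the producers of these questionnaires will be followed".

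Change from baseline is then analysed by MMRM with time-point, baseline value and their interaction (SAP 8.1.2 and 8.2.5). On missing scores, SAP 8.1.2 says: "Any missing observations will be set to missing and the MMRM model will assume data are missing at random". By-visit summaries of absolute values and changes are also planned (SAP 8.2.3.2).

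Neither document makes an exception for a patient who worked no hours.

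**The concern.** The completeness rule treats Q5 as necessary in every case. The formula does not: once no hours are worked and some are missed, Q5 carries no weight and the score is known. Requiring Q5 in that case discards a known score, and that score is the maximum of the scale.

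Missingness of this kind depends on the value that is lost. The MMRM for work productivity loss contains only time-point, baseline and their interaction. The patient's 100% absenteeism at the same visit is observed but is not in that model, so the model has no direct means of recovering the lost value. If the blank falls at baseline, there is neither a baseline covariate nor a change score, and the patient leaves that domain's MMRM.

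Work productivity is one of the reasons given for the study (Protocol section 7), and change in WPAI is secondary endpoint j in Protocol 8.1.2. Only patients in work contribute to this score, so it rests on fewer than the roughly 200 planned patients, and a few lost maximum scores could shift a mean.

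**Working it through.** The plan states no figure for this score (no WPAI sample size, expected mean or expected share of absent workers), so there is nothing to reproduce. The check is algebra on the SAP formula, followed by an illustration with assumed inputs.

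**Formula (SAP 6.1.2.10).** Let A = Q2/(Q2 + Q4). Work productivity loss = {A + (1 − A) × Q5/10} × 100.

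**Step 1: no hours worked, some hours missed (Q4 = 0, Q2 > 0).** A = Q2/Q2 = 1, so the score is {1 + 0 × Q5/10} × 100 = 100%. Evaluated at Q2 = 1, 8, 20 and 40 and at every Q5 from 0 to 10, it is 100.0% each time.

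**Step 2: some hours worked.** Q5 is then needed:
- Q2 = 20, Q4 = 20: A = 0.5, and the score runs from 50% (Q5 = 0) to 100% (Q5 = 10).
- Q2 = 39, Q4 = 1: A = 0.975, and the score runs from 97.5% to 100%.

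The rule is therefore sound here, and only the Q4 = 0 case needs an exception.

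**Step 3: no hours worked and none missed (Q2 = Q4 = 0).** A = 0/0, so absenteeism and work productivity loss are both undefined. The SAP does not say how to handle this.

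**Step 4: effect on a by-visit mean.** Assume that a share s of workers is in the Step 1 state with Q5 blank, and that the other workers average 40%. Neither figure is in the documents. Mean with these patients kept = 40(1 − s) + 100s; mean under the current rule = 40%.

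| Assumed share s | Mean if kept | Mean under the rule | Understatement (points) |
|---|---|---|---|
| 3% | 38.8 + 3 = 41.8% | 40% | 1.8 |
| 5% | 38 + 5 = 43.0% | 40% | 3.0 |
| 10% | 36 + 10 = 46.0% | 40% | 6.0 |

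The mean is understated whenever the other workers average below 100%.

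**Step 5: effect on change from baseline.** Assume that the other workers go from 50% to 35%, so the change is −15 points with the Step 1 patients dropped. With them kept:
- Share falls from 10% to 5%: baseline 45 + 10 = 55, follow-up 33.25 + 5 = 38.25, change −16.75.
- Share stays at 5%: baseline 47.5 + 5 = 52.5, follow-up 38.25, change −14.25.
- Share rises from 5% to 10%: baseline 52.5, follow-up 31.5 + 10 = 41.5, change −11.0.

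The error can go either way. These are differences of raw means, not MMRM estimates, which also condition on baseline and use the other visits.

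**Step 6: coherence between domains.** By the formula, a patient's work productivity loss can never be below that patient's absenteeism. Under the rule, a Step 1 patient with Q5 blank counts as 100% in one domain and as missing in the other. Suppose 10% of workers are in this state and the others average 5% absenteeism and 12% work productivity loss (all assumed). Reported absenteeism is 0.9 × 5 + 10 = 14.5%, but reported work productivity loss is 12%, an ordering that cannot occur when both are computed on the same patients.

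**The case against.** **The blank is inferred.** The documents give only a label for Q5. They reproduce neither the item, nor a skip instruction, nor a data-entry rule. If a patient with zero hours does answer Q5, the score is kept at 100% and nothing is lost. This stands. Protocol 9.9 expects incomplete questionnaires in general, but that does not show that this item is blank in this group. The point is therefore conditional, though the proposed rule does no harm if the blank never occurs.

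**The rule is the instrument's own.** The SAP cites the developers' coding guidance, and following published scoring helps comparison with other WPAI results. That is a defensible reason for the rule, and this is an improvement to it rather than a sponsor error. It does not alter the algebra: at Q4 = 0 and Q2 > 0, Q5 is not needed to obtain the score.

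**A reader might infer that the plan drops the most impaired workers.** The documents do not support that:
- Only one of four domains is affected, and only at that visit. Absenteeism (100%) and activity impairment are still scored.
- A worker with Q5 = 10 also scores 100% and is kept, so worst scores are not removed as a class.
- The formula has no term for usual hours, so one missed hour with none worked gives the same 100% as 40 missed hours. A score of 100% does not by itself identify the most impaired.

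**A reader might also infer a bias of known direction in the treatment-related change.** Step 5 shows otherwise: the sign depends on how the share in this state moves between visits.

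**The consequence is limited.** WPAI is one of 13 listed secondary endpoints, SAP section 4 states that there are no formal hypotheses or decision rules, and the sample size does not depend on it. This stands and sets the weight of the point.

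**Conclusion.** The point holds in conditional form. For a patient with Q4 = 0 and Q2 > 0, the formula fixes work productivity loss at 100%, and the completeness rule discards that score if Q5 is blank. By-visit means would then be understated, by 1.8 to 6.0 points for an assumed share of 3% to 10% and an assumed 40% average in the other workers. Change from baseline could be biased in either direction, and a patient affected at baseline is lost to that domain's MMRM.

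The algebra is certain. The frequency of the blank, the share of workers affected and the average in the others are assumptions that the documents cannot settle. Nothing here touches the primary analysis. It is a low-priority improvement, worth making because it is cheap and uses data already collected.

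**What to change.** Amend SAP 6.1.2.10 and 7.1.4 to state:

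- If Q4 = 0 and Q2 > 0, work productivity loss is 100% regardless of Q5. Presenteeism stays missing when Q5 is blank.
- If Q2 = Q4 = 0, absenteeism and work productivity loss are missing, because the ratio is undefined.
- In all other cases the current completeness rule applies.
- The number of patients in each of the two zero-hours states is reported at each visit, so that readers can see how much the rule matters.

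The cost is a few sentences in the SAP and a small departure from the scoring text it cites, which should be declared as such. No new data, visits or questionnaire items are needed.

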6.1.2.11. Patient satisfaction with Treatment

Patient's satisfaction with treatment is assessed at Baseline and the final visit (month 12) on a 5-point scale (where 0 = very dissatisfied and 4 = very satisfied).

6.1.2.12. Patient Global Assessment (PtGA)

Patient Global Assessment (PtGA) is measured using a visual analogue scale (VAS) on a 0-100 mm scale, where 0 mm = no symptoms of disease and 100 mm = maximum seriousness which a patient can imagine. PtGA is measured at each time point (Baseline, Month 3, 6 and 12).

6.1.2.13. Physician Global Assessment (PhGA)

Physician Global Assessment (PhGA) is measured using a VAS on a 0-100 mm scale (where 0 = no disease activity and 100 = maximum disease activity) at each time point (Baseline, Month 3, 6 and 12).

6.2. Safety Endpoints

The reporting of safety data will be in accordance with Pfizer Data Standards.

Safety endpoints in this study include the incidence of all adverse events (AEs) and serious adverse events (SAEs). These will be summarized by the treatment group 'Tofacitinib' (see [Section 8.2.2](#)).

The treatment patterns of RA patients prescribed Tofacitinib in a real-world setting will also be described. Patients will be classified into 6 discrete categories as follows:

1. Tofa Mono

Patients who receive Tofacitinib as a monotherapy throughout the study.

2. Tofa Combo

Patients who receive Tofacitinib in combination with another DMARD throughout the study.

3. Tofa Mono to Combo

Patients who start the study receiving Tofacitinib as a monotherapy and then switch to Tofacitinib in combination with another DMARD.

4. Tofa Combo to Mono

Patients who start the study receiving Tofacitinib in combination with another DMARD and then switch to Tofacitinib as a monotherapy.

5. Tofa Mono to Other Treatment

Patients who start the study receiving Tofacitinib as a monotherapy and then discontinue Tofacitinib and switch to another DMARD.

6. Tofa Combo to Other Treatment

Patients who start the study receiving Tofacitinib in combination with another DMARD and then discontinue Tofacitinib.

The duration of treatment with Tofacitinib (in days) will be calculated as:

Date of permanent Tofacitinib discontinuation – Start Date of Tofacitinib treatment + 1

In addition, the time to first treatment change will be calculated:

Date of treatment change – Study Start Date + 1

Where a treatment change is defined as the start of a new treatment or the discontinuation of a current treatment.

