8.2.2. Safety Analyses

Safety data will be presented in tabular and/or graphical format and summarized descriptively, where appropriate. Safety data will be summarized according to Pfizer standards.

Adverse events will be reported according to the 3-tier approach.

Two sets of 'All Causality' and 'Treatment Emergent' adverse events will be summarised. The first set will contain adverse event data for patients while they were taking Tofacitinib. This AE table will summarise AEs under one treatment heading for Tofacitinib (which includes monotherapy and combination therapy). A drug lag of 28 days will be used to assign treatment emergence to Tofacitinib. The AE listings will also list the individual drugs that were being taken at the time of the AE. The second set will include a separate listing of AEs which occurred under another DMARD, following cessation of Tofacitinib. For the cases where the patient continues to be observed for the full duration of the study following discontinuation of Tofacitinib.

NOTE: A lag of 28 days will be applied following cessation of Tofacitinib in the first table. The non-Tofacitinib listing will apply a drug lag of 0 days. Therefore an event which starts on the first day of a new treatment, e.g. Enbrel will be assigned to Tofacitinib in the first table if the AE is within 28 days of Tofacitinib, and also in the listing as the AE started after the initiation of Enbrel. Therefore any event which occurs during a 28 day lag of discontinuing Tofacitinib will appear under Tofacitinib in the first table, and under the new treatment in the listing.

The treatment patterns of RA patients (as defined in [Section 6.2](#)) and the duration of Tofacitinib treatment will be summarized to include n and the percentage in each treatment pattern category. The time to first treatment change (as defined in [Section 6.2](#)) will also be summarized overall and by treatment pattern.

Safety analyses will use the Safety Analysis Set.

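### Tofacitinib duration and time to first treatment change have no rule for patients who do not stop or change, so read literally their summaries describe only stoppers and changers

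*SAP*

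**What the plan says.** SAP 6.2 sorts patients into six treatment patterns and then defines two times.

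- **Duration of tofacitinib, in days:** "Date of permanent Tofacitinib discontinuation – Start Date of Tofacitinib treatment + 1".
- **Time to first treatment change:** "Date of treatment change – Study Start Date + 1". The section adds: "Where a treatment change is defined as the start of a new treatment or the discontinuation of a current treatment".

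Two of the six patterns are defined by staying on one regimen: "Patients who receive Tofacitinib as a monotherapy throughout the study" and "Patients who receive Tofacitinib in combination with another DMARD throughout the study". Two more are moves between monotherapy and combination while tofacitinib continues. Only the last two patterns involve leaving tofacitinib.

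SAP 8.2.2 states that the patterns and the duration "will be summarized to include n and the percentage in each treatment pattern category", and that time to first change "will also be summarized overall and by treatment pattern". It names no statistics for the two times, so the SAP 8.1.2 default for continuous variables applies: n, mean, SD, median, minimum and maximum. Neither section sets an end date or censoring rule for a patient who completes Month 12 on drug, withdraws, dies or is lost. *Study Start Date* is not defined.

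**The concern.** Both quantities are times to an event within a planned 12 months of observation per patient, and many patients may not have the event. A formula that needs the event date gives those patients no value. For duration, the patients left out are the ones treated longest.

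The planned table also cannot be filled from the planned formula. Time to first change is to be shown by pattern, yet a patient on one regimen throughout ordinarily has no change date. The *overall* row would then mean overall among changers.

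Describing treatment patterns is the first secondary objective (Protocol 8) and key secondary endpoint m (Protocol 8.1.2), and Protocol 9.7 leaves detailed methods to the SAP. A reader of the report would naturally take a mean duration as time on drug in this cohort. If it covers stoppers only, it answers a different question.

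**Working it through.** **The plan's own figure.** The documents state no figure for duration, persistence or time to change. Their only design calculation is the sample size in Protocol 9.5: N = 10k/p = 10 × 10 / 0.50 = 200. It reproduces, and is used here only to turn percentages into patients.

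**Which patients get a value under the formulas.**

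- Duration: ordinarily only the two patterns that leave tofacitinib. The four patterns that remain on it have no permanent discontinuation date.
- Time to first change: patients who move between monotherapy and combination have a value while still on tofacitinib, as do patients who stop. The two unchanged patterns ordinarily have none.

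**Size for duration if patients without a date are left out.** The assumptions are that a proportion d stops by day 365, that the hazard is constant, and that there is no other loss. The formulas are:

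- hazard λ = −ln(1 − d) / 365
- restricted mean to day 365, all patients: R = d / λ
- mean among stoppers: M = [R − 365(1 − d)] / d

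For d = 0.20: λ = 0.2231/365 = 0.000611; R = 327.1; M = (327.14 − 292)/0.20 = 175.7.

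For d = 0.40: λ = 0.5108/365 = 0.001400; R = 285.8; M = (285.81 − 219)/0.40 = 167.0.

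| Stopping by day 365 (assumed) | No duration, of 200 | Mean, stoppers only | Restricted mean, all | Shortfall |
|---|---|---|---|---|
| 10% | 180 | 179 | 346 | 48% |
| 20% | 160 | 176 | 327 | 46% |
| 30% | 140 | 172 | 307 | 44% |
| 40% | 120 | 167 | 286 | 42% |
| 60% | 80 | 155 | 239 | 35% |

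From 60% stopping down to 10%, the restricted mean rises by 107 days (239 to 346), but the stoppers-only mean rises by only 24 (155 to 179). The literal summary therefore says little about persistence, and the gap is widest when persistence is best.

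**Sensitivity to the hazard.** With a Weibull shape of 0.7 (early stopping) and 20%, 40% and 60% stopping, the pairs are 143 vs 321, 135 vs 273 and 122 vs 219 days. With shape 1.5 (late stopping) they are 213 vs 335, 205 vs 301 and 194 vs 262. The shortfall runs from 26% to 55%.

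**Time to first change.** The same formulas hold with d read as the proportion with a change. Stopping tofacitinib is itself a change, so at least as many patients have a value here as for duration. The documents give no rate.

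**Origin.** Inclusion criterion 3 (Protocol 9.2.1) allows at most seven working days on tofacitinib, which is 9 to 11 calendar days depending on the weekday. If *Study Start Date* means enrolment, times are shortened by at most about 11 days. If it meant the calendar start of the study (May 2020, Protocol 9.2), times would be lengthened by up to about 365 days over the 12-month recruitment, and by 365/2 = 182.5 days on average under uniform enrolment.

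**The case against.** The strongest reply is that the SAP is silent on patients without a date and does not exclude them. A programmer could supply an end date, and SAP 6.2 refers safety reporting, the section where these items sit, to sponsor data standards that are not part of the documents. This stands to the extent that a reader may not infer as a fact that persistence will be badly understated. The understatement is conditional on following the formulas as written. It does not remove the point, because no end-date rule appears in either document and the SAP is where one belongs.

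Second, the main description of treatment patterns is the count and percentage in each category, on the Safety Analysis Set. That output is sound and shows who stayed on tofacitinib, though not for how long those who left had been treated. It would be wrong to say that the whole treatment-pattern description covers stoppers only.

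Third, a reader might take the undefined origin as a further large error in the same direction. The text does not support that. SAP 6.2 speaks of starting the study at patient level, and SAP Appendix A1.1 places enrolment at Day 1, so enrolment is the natural reading. The calendar reading is strained, and it would lengthen times, not shorten them.

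Fourth, the study has no formal hypotheses (SAP 4) and its secondary objectives are descriptive unless stated otherwise (SAP 2.4), so a survival method may look like a preference. A bare end-date rule would give every patient a number. But a plain mean or median would then mix completed durations with durations cut off by the end of follow-up. Kaplan-Meier is itself descriptive and keeps the two apart.

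**Conclusion.** The point holds in conditional form. The two formulas give no value to patients without a stop or a change, and no censoring rule or time-to-event method is stated. If they are applied as written, duration describes stoppers, time to change describes changers, and both understate what is typical of the cohort.

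For duration, the shortfall in the mean is 42-46% at 20-40% stopping under a constant hazard, and 26-55% over the Weibull shapes tried at 20-60% stopping. These sizes rest on assumed discontinuation rates and on patients without a date being left out. No separate size can be given for time to first change. The undefined origin is a lesser fault, worth days under its natural reading.

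The pattern percentages, the primary analysis and the sample size are not affected. This should be settled in the SAP before the tables are programmed.

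**What to change.** Amend SAP 6.2 and 8.2.2 as follows.

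- **One origin.** Measure both times from the tofacitinib start date, and remove or define *Study Start Date*.
- **Censoring.** Censor a patient without the event at Month 12, withdrawal, death or last contact, whichever comes first.
- **Summary.** Report Kaplan-Meier estimates for both: the proportion still on tofacitinib, and the proportion unchanged, at months 3, 6 and 12; the median if reached (under 50% with the event by day 365, it will not be); and the restricted mean to day 365.
- **Keep the pattern table.** Show these beside the number and percentage per treatment pattern. If times among stoppers or changers are also shown, label them as such.

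The cost is SAP wording and one additional table. No new data are needed: the start of tofacitinib is a listed variable (Protocol 9.3), and DMARD stop and start dates are documented at visits (Protocol 9.4.13).
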